#### 5.4 Laboratory parameters derivations

The following table provides an overview for which lab parameters a CTCAE v5 grade is defined and used in this study. The respective limits can be found in:

*https://ctep.cancer.gov/protocoldevelopment/electronic\_applications/docs/CTCAE\_v5\_Quick\_Reference\_5x7.pdf* 

#### Hematology:

Parameter	Grades defined in CTCAE, Version 5.0
Hematocrit	No
Hemoglobin	Yes (see CTCAE term "anemia")
MCH (mean corpuscular hemoglobin)	No
MCV (mean corpuscular volume)	No
Platelets	Yes ("Platelet count decreased")
Red blood cells (RBCs)	No
White blood cells (WBC)	Yes ("White blood cell decreased")
Basophils (rel.)	No
Eosinophils (rel.)	No
Lymphocytes (rel.)	No
Monocytes (rel.)	No
Band Neutrophils (rel.)	No
Segmented Neutrophils (rel.)	No
MCHC (mean corpuscular hemoglobin concentration)	No
Basophils (abs.)	No
Eosinophils (abs.)	No
Lymphocytes (abs.)	Yes (maximum grade of "Lymphocyte count decreased" and "Lymphocyte count increased")
Monocytes (abs.)	Yes ("Neutrophil count decreased")
Band Neutrophils (abs.)	No
Segmented Neutrophils (abs.)	No
differential other (rel.)	No
differential other (abs.)	No

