Options for salvage therapy include retreatment with corticosteroids, a combination of first-line agent(s), or treatment with a second-line agent. Long-term administration of corticosteroids is limited by the development of side effects, including peripheral edema, hypertension, heartburn/peptic ulcers, anxiety, insomnia, agitation, Cushingoid features, diabetes, cataracts, potassium loss, osteoporosis, and other adverse experiences. Furthermore, corticosteroid-treated patients are at increased risk of infections (Portielje et al 2001, Stasi et al 1995, Pizzuto and Ambriz, 1984).

While corticosteroids remain the standard of care, high relapse rates and considerable toxicity associated with long-term corticosteroid use highlight a significant unmet medical need in management of first-line ITP. Novel therapeutic approaches are warranted that achieve durable responses and reduce the need for long-term corticosteroid use.

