#### 2.8.3 Laboratory data

All laboratory data will be listed by treatment group, subject, and visit (including the safety follow-up visits). Values outside the center-specific normal range are flagged as "low" or "high", as well as clinically significant abnormalities and CTCAE grades, if applicable. Summary statistics will be provided by treatment group and visit. Changes are calculated from baseline to the last on-treatment value. Again (see Adverse events (AEs)2.8.1) the on-treatment period lasts from the date of first dose of study treatment with eltrombopag or dexamethasone

(whichever is first) to 30 days after the date of the last dose of study treatment (whichever is last).

Boxplots will be presented for the total study course separated by treatment group in addition.

Grading of laboratory values will be assigned programmatically as per NCI Common Terminology Criteria for Adverse Events (CTCAE) version 5.0. The calculation of CTCAE grades will be based on the observed laboratory values only, clinical assessments will not be taken into account. CTCAE Grade 0 will be assigned for all non-missing values not graded as 1 or higher. Grade 5 will not be used. For laboratory tests where grades are not defined by CTCAE v5.0, results will be categorized as low/normal/high based on laboratory normal ranges.

For laboratory tests where grades are defined by CTCAE v5.0,

- Worst post-baseline CTCAE grade (regardless of the baseline status). Each subject will be counted only once for the worst grade observed post-baseline.
- Shift tables using CTCAE v5.0 grades to compare baseline to the worst on-treatment value

For laboratory tests where grades are not defined by CTCAE v5.0,

Shift tables using the low/normal/high/ (low and high) classification to compare baseline to the worst on-treatment value.

Any significant findings in laboratory will be documented as AEs and reported as such. Laboratory data reported in the eCRF section of Adverse Events (labeled as "relevant laboratory results regarding this AE") are listed only.

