#### **Chemistry**:

Albumin	Yes ("Hypoalbuminemia")
Alkaline phosphatase	Yes ("Alkaline phosphatase increased")
ALT (alanine aminotransferase)	Yes ("Alanine aminotransferase increased")
AST (aspartate transaminase)	Yes ("Aspartate aminotransferase increased")
Amylase	Not applicable, because CTCAE grading includes the information about "asymptomatic", "signs and symptoms"
Bicarbonate	No
Calcium	Yes ("Hypocalcemia")
Chloride	No
Creatinine	Yes ("Creatinine increased")
Creatinine kinase	Yes ("CPK increased")
Direct bilirubin	Yes ("Blood bilirubin increased")
Total bilirubin	No
LDH (lactate dehydrogenase)	No
Lipase	Not applicable, because CTCAE grading includes the information about "asymptomatic"
Lipase Glucose (fasting)	Not applicable, because CTCAE grading includes the information about "asymptomatic" Yes ("Hypoglycemia")
Lipase Glucose (fasting) GGT	Not applicable, because CTCAE grading includes the information about "asymptomatic"         Yes ("Hypoglycemia")         Yes ("GGT increased")
Lipase Glucose (fasting) GGT Magnesium	Not applicable, because CTCAE grading includes the information about "asymptomatic"Yes ("Hypoglycemia")Yes ("GGT increased")Yes ("Hypermagnesemia" or "Hypomagnesemia" )
Lipase Glucose (fasting) GGT Magnesium Phosphorus	Not applicable, because CTCAE grading includes the information about "asymptomatic"Yes ("Hypoglycemia")Yes ("GGT increased")Yes ("Hypermagnesemia" or "Hypomagnesemia" )No
Lipase Glucose (fasting) GGT Magnesium Phosphorus Potassium	Not applicable, because CTCAE grading includes the information about "asymptomatic"Yes ("Hypoglycemia")Yes ("GGT increased")Yes ("Hypermagnesemia" or "Hypomagnesemia" )NoYes ("Hyperkalemia" or "Hypokalemia")
Lipase Glucose (fasting) GGT Magnesium Phosphorus Potassium Sodium	Not applicable, because CTCAE grading includes the information about "asymptomatic"Yes ("Hypoglycemia")Yes ("GGT increased")Yes ("Hypermagnesemia" or "Hypomagnesemia" )NoYes ("Hyperkalemia" or "Hypokalemia")No
Lipase Glucose (fasting) GGT Magnesium Phosphorus Potassium Sodium Total protein	Not applicable, because CTCAE grading includes the information about "asymptomatic"Yes ("Hypoglycemia")Yes ("GGT increased")Yes ("Hypermagnesemia" or "Hypomagnesemia" )NoYes ("Hyperkalemia" or "Hypokalemia")NoNoNoNoNoNoNoNoNoNoNoNoNo

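### Absolute lymphocytes get one pooled CTCAE grade, so the worst-grade and shift tables do not separate falls from rises; the rule for potassium and magnesium is unstated

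*SAP*

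**What the plan says.** SAP 5.4 introduces its laboratory tables as an overview of "for which lab parameters a CTCAE v5 grade is defined and used in this study". In the Hematology table, absolute lymphocytes are graded by the "maximum grade of 'Lymphocyte count decreased' and 'Lymphocyte count increased". In the Chemistry table, potassium has one row naming "Hyperkalemia' or 'Hypokalemia" and magnesium has one row naming "Hypermagnesemia' or 'Hypomagnesemia". Neither chemistry row mentions a maximum, and neither says that the two terms are tabulated separately.

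SAP 2.8.3 then assigns the outputs. Tests with a CTCAE grade get a worst-grade table, where "Each subject will be counted only once for the worst grade observed post-baseline", and "Shift tables using CTCAE v5.0 grades to compare baseline to the worst on-treatment value". The low/normal/high shift table comes under a separate lead-in, "For laboratory tests where grades are not defined by CTCAE v5.0". No rule splits a graded test by direction.

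The same section also plans laboratory listings with low/high flags, summary statistics by group and visit, changes from baseline to the last on-treatment value, and boxplots by group.

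**The concern.** A lymphocyte count can be abnormal in either direction, and the two directions are different findings. Once they share one grade, a low and a high value of equal grade fall in the same table cell. A patient who moves from a Grade 1 high value to a Grade 2 low value appears simply as having worsened.

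Laboratory changes belong to the safety objective (number 9 in Table 2-1 of the protocol), and after Amendment 3 all analyses are descriptive. The safety tables are therefore useful only for how clearly they describe what happened in each arm. Tests without a CTCAE grade, such as sodium and chloride (both marked 'No' in SAP 5.4), keep direction in their shift table. A test graded in both directions loses it.

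**Working it through.** The plan gives no figure to reproduce. The check sets the rules side by side and then counts how much direction the pooled grade removes.

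**Step 1: inputs**

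| Parameter | Rule in SAP 5.4 | Pooling |
|---|---|---|
| Lymphocytes (abs.) | maximum of the decreased and increased grades | explicit |
| Potassium | two terms joined by 'or', one row | inferred |
| Magnesium | two terms joined by 'or', one row | inferred |

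All three are graded tests, so under SAP 2.8.3 each gets the worst-grade table and the grade shift table, and not the low/normal/high shift table.

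**Step 2: what pooling removes**

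Write a signed grade s from -4 (low) to +4 (high). The pooled grade is |s|, from 0 to 4. SAP 2.8.3 assigns Grade 0 to ungraded values and does not use Grade 5. That both directions use all of grades 1 to 4 is an assumption, because the documents do not reproduce the CTCAE limits.

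- Signed baseline-to-worst combinations: 9 x 9 = 81.
- Pooled shift cells: 5 x 5 = 25.
- Cells holding more than one direction pattern: all except 0 to 0, so 25 - 1 = 24.
- Example: the cell 2 to 2 holds low-low, low-high, high-low and high-high.

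Now relax the assumption. Let one direction use grades 1 to 4 and let the other share only k of them. A cell is unmixed only if neither its row grade nor its column grade is shared, so the number of mixed cells is 25 - (5 - k)^2:

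- k = 4: 25 - 1 = 24
- k = 3: 25 - 4 = 21
- k = 2: 25 - 9 = 16
- k = 1: 25 - 16 = 9

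In the worst-grade table, k of the grades are mixed. Direction is lost to some degree whenever at least one grade is shared. This counts table cells. It says nothing about how many patients would be affected.

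**Step 3: potassium and magnesium**

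Two things point to pooling: there is one row per parameter under an introduction that speaks of a single grade, and each subject is counted once in the worst-grade table. One thing points the other way: the authors wrote 'maximum' for lymphocytes and did not write it here. The text does not settle the matter.

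**Step 4: where direction survives**

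- Listings: low/high flags per patient, but no counts by arm.
- Visit summaries and boxplots: direction of the distribution, but opposite movements can offset in the mean, and patients with low or high abnormalities are not counted.
- Change from baseline: taken to the last on-treatment value, not the worst.
- Adverse event tables: counts by preferred term, but only for laboratory findings judged significant enough to report as events.

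**The case against.** The strongest reply is that direction is not lost from the report. With about 24 patients, a reader can go through the flagged listings, and the visit summaries and boxplots show which way values moved. This stands, and it limits the point to two table types. A reader might infer that the analysis cannot show direction at all, and the documents do not support that.

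A second reply is that protocol 12.5.2 opens its laboratory paragraph with low/normal/high shift tables for laboratory data in general, that SAP 2.8 refers to that section, and that SAP 4 declares no change from the protocol. This stands in part. The later bullets of 12.5.2 confine those tables to ungraded tests, as SAP 2.8.3 does, so the opening sentence creates an ambiguity and does not clearly supply the missing table.

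A third reply is that only lymphocytes are explicitly merged. This is correct. A reader might infer that all three parameters are pooled by rule, but for potassium and magnesium this is a reading of 'or'.

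A reader might also build a harm argument on potassium, because protocol 1.1.1 lists "potassium loss, osteoporosis, and other adverse experiences" among steroid effects. That list concerns long-term corticosteroid use, whereas this trial gives 4-day courses, one in Arm A and at most three in Arm B. Protocol 4.5.1 names renal tubular toxicity as a potential eltrombopag risk but ties it to no direction of potassium or magnesium change. The documents do not support a potassium-specific consequence.

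**Conclusion.** The point holds for absolute lymphocytes: the pooling is written into SAP 5.4, and the two grade tables in SAP 2.8.3, as specified, do not show direction. For potassium and magnesium the finding is that the rule is not stated. Pooling is the more natural reading but is not proven.

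The size is small. Under the 0-to-4 assumption, 24 of 25 shift cells mix directions, and between 9 and 24 do if the two terms share only one to four grades. The effect is on the clarity of the safety tables. Other planned output carries direction, but none clearly gives the number of patients per arm with a low and with a high graded abnormality. The primary endpoint and the sample size are not affected. Nothing in the documents predicts opposite laboratory patterns in the two arms, so no size of distortion can be given.

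**What to change.** In SAP 5.4, replace the maximum rule for absolute lymphocytes with two derived grades, one for the decreased term and one for the increased term. Present each as its own block in the worst-grade table and in the CTCAE shift table of SAP 2.8.3, with each subject counted once per direction. In the Chemistry table, state that the high and low terms for potassium and for magnesium are graded and tabulated separately in the same way.

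This needs no new data. It costs a few lines of programming and, for each of the three parameters, one extra block in each of the two tables. With about 24 patients these blocks will be sparse, which is acceptable in a descriptive report.

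### SAP 5.4 grades monocytes on the neutrophil criterion and direct rather than total bilirubin, so the CTCAE-graded laboratory tables leave neutropenia and total bilirubin rises without a grade

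*SAP*

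**What the plan says.** SAP 5.4 introduces its tables as an "overview for which lab parameters a CTCAE v5 grade is defined and used in this study".

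- **Hematology.** The entry for absolute monocytes is "Monocytes (abs.) Yes ('Neutrophil count decreased". The neutrophil rows are not graded: "Band Neutrophils (abs.) No" and "Segmented Neutrophils (abs.) No", and likewise for the two relative counts.
- **Chemistry.** The entries are "Direct bilirubin Yes ('Blood bilirubin increased" and "Total bilirubin No".

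SAP 2.8.3 says how the tables are used: "Grading of laboratory values will be assigned programmatically", following CTCAE v5.0. Tests with a defined grade go into worst post-baseline grade tables and grade-shift tables, with the rule "CTCAE Grade 0 will be assigned for all non-missing values not graded as 1 or higher". Tests without a defined grade are classified only as low, normal or high.

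Protocol 6.5.2 names CTCAE v5.0 for grading both adverse events and laboratory results. Protocol 12.5.2 prespecifies the same worst-grade and shift tables, and SAP section 4 declares no departure from the protocol's analyses.

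**The concern.** A neutrophil term cannot grade a monocyte count. Protocol Table 8-3 collects the two as separate items of the differential, so nothing in the data forces the substitution.

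The bilirubin entry disagrees with the protocol. Table 6-5, whose first column is headed as the worst CTCAE grade, sets its bilirubin bands on total bilirubin. The drug-induced liver injury criteria in 6.5.3.1 also use total bilirubin.

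Both areas matter for safety here. SAP 2.8.1 names hepatobiliary laboratory abnormalities as events of special interest, and SAP 5.3 lists neutropenias. Protocol 4.5.1 reports rises in indirect bilirubin with eltrombopag, which a grade based on direct bilirubin would not show. Under Protocol 10.1.1 an abnormal value becomes an adverse event only if it causes signs or symptoms, is considered clinically significant or needs therapy. The graded laboratory tables are therefore the severity summary that does not depend on the investigator's decision to report.

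**Working it through.** The plan gives no figure to reproduce. The check is a row count and a comparison of sections.

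**1. Hematology rows in SAP 5.4.** There are 22 rows. Five are marked as graded: hemoglobin, platelets, white blood cells, absolute lymphocytes and absolute monocytes.
- Graded rows carrying another cell type's criterion: 1 of 5 (monocytes).
- Neutrophil rows: band and segmented, each relative and absolute, which makes 2 × 2 = 4. Graded: 0 of 4.

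**2. Bilirubin in the two documents.**

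| Source | Direct bilirubin | Total bilirubin |
|---|---|---|
| SAP 5.4 | graded (blood bilirubin term) | not graded |
| Protocol Table 6-5 (CTCAE-grade heading) | not banded | four bands: >ULN–1.5, >1.5–3.0, >3.0–10.0, >10.0 × ULN |
| Protocol 6.5.3.1 | among the follow-up tests only | part of the criteria |

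**3. What the fallback does to total bilirubin.** All four bands lie above ULN. Under the low/normal/high rule each becomes high, so 4 categories become 1. A value of 1.2 × ULN (first band) and one of 11 × ULN (fourth band) fall in the same cell of the shift table.

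**4. Worked case, taken from a situation that Table 6-5 itself describes.** Total bilirubin is 5 × ULN and the rise is due to the indirect component only.
- Table 6-5: >3.0–10.0 × ULN, the third of four bands.
- SAP, total bilirubin: no grade, shown as high.
- SAP, direct bilirubin: within range by construction. If a grade starts above ULN, as the first band of Table 6-5 does, the grade-0 rule in SAP 2.8.3 applies and the bilirubin grade is 0.

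**5. Could the PDF reading have shifted the column?** The neighbouring rows are sensibly paired: absolute lymphocytes with lymphocyte terms, creatinine kinase with the CPK term, and LDH not graded. Both wrong entries come before the point where the chemistry table visibly breaks up (lipase and glucose). A uniform shift would have displaced these neighbours too.

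**Not computable.** The number of monocyte values that would be wrongly graded cannot be given, because the SAP cites the CTCAE limits only by a link.

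**The case against.** The strongest reply is that little information is lost.

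- The worked patient should still appear with a CTCAE grade. Table 6-5 attaches a dose change to that case, Protocol 8.4.2 sends clinically relevant values that require a dose change to the adverse event page, and SAP 2.8.1 tabulates those events by maximum CTCAE grade.
- A value of 11 × ULN would stand out in the by-visit summary statistics, which include the maximum, and in the boxplots.
- Protocol 4.5.1 reports indirect bilirubin rises but does not call them isolated.
- The bilirubin half is an inference from Table 6-5, since neither document reproduces the CTCAE definition; the monocyte error needs no inference.
- SAP 2.8.3 invokes CTCAE v5.0 itself, and 5.4 calls itself an overview, so a careful programmer might not code it literally.
- A local displacement in the PDF cannot be excluded entirely.
- About 24 patients are expected and all analyses are descriptive.

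Most of this stands, and it limits how much the error matters. It does not make the table right. The adverse event route depends on reporting, and summary statistics and boxplots do not count patients by grade. Section 5.4 states which grades are used in this study, and nothing elsewhere in the SAP corrects it.

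**Conclusion.** The concern holds. SAP 5.4 is wrong on its face for monocytes and neutrophils, and it conflicts with the protocol on bilirubin. If it is programmed as written, the worst-grade and grade-shift tables will contain monocyte counts graded as neutrophils, no graded neutrophil count (0 of 4 rows), and no graded total bilirubin (four protocol bands reduced to one category).

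The effect stops at those tables. Listings, flags, low/normal/high tables, summary statistics, boxplots, adverse event and special-interest tables, patient management and efficacy are untouched.

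The conclusion assumes that the extracted rows match the original PDF, that the program follows 5.4, and, for the grade-0 example, that bilirubin grading starts above ULN. The error should be fixed, because the affected tables are prespecified safety output and the correction is cheap.

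**What to change.** In SAP 5.4:

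- Set absolute monocytes to not graded.
- Apply the neutrophil term to the total absolute neutrophil count, and state how band and segmented counts are combined to form it.
- Move the blood bilirubin term from direct to total bilirubin, and show direct bilirubin as low/normal/high.
- Check these rows against the original PDF, and these and all remaining rows against CTCAE v5.0.

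The SAP history says that version 3.0 was agreed before database lock and signed shortly after it, so graded tables may already exist. Any produced from this map should be rerun and the correction documented. The cost is a few table rows, the matching program lines and one rerun of the graded laboratory tables. No new data are needed.

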#### **Chemistry**:

Albumin	Yes ("Hypoalbuminemia")
Alkaline phosphatase	Yes ("Alkaline phosphatase increased")
ALT (alanine aminotransferase)	Yes ("Alanine aminotransferase increased")
AST (aspartate transaminase)	Yes ("Aspartate aminotransferase increased")
Amylase	Not applicable, because CTCAE grading includes the information about "asymptomatic", "signs and symptoms"
Bicarbonate	No
Calcium	Yes ("Hypocalcemia")
Chloride	No
Creatinine	Yes ("Creatinine increased")
Creatinine kinase	Yes ("CPK increased")
Direct bilirubin	Yes ("Blood bilirubin increased")
Total bilirubin	No
LDH (lactate dehydrogenase)	No
Lipase	Not applicable, because CTCAE grading includes the information about "asymptomatic"
Lipase Glucose (fasting)	Not applicable, because CTCAE grading includes the information about "asymptomatic" Yes ("Hypoglycemia")
Lipase Glucose (fasting) GGT	Not applicable, because CTCAE grading includes the information about "asymptomatic"         Yes ("Hypoglycemia")         Yes ("GGT increased")
Lipase Glucose (fasting) GGT Magnesium	Not applicable, because CTCAE grading includes the information about "asymptomatic"Yes ("Hypoglycemia")Yes ("GGT increased")Yes ("Hypermagnesemia" or "Hypomagnesemia" )
Lipase Glucose (fasting) GGT Magnesium Phosphorus	Not applicable, because CTCAE grading includes the information about "asymptomatic"Yes ("Hypoglycemia")Yes ("GGT increased")Yes ("Hypermagnesemia" or "Hypomagnesemia" )No
Lipase Glucose (fasting) GGT Magnesium Phosphorus Potassium	Not applicable, because CTCAE grading includes the information about "asymptomatic"Yes ("Hypoglycemia")Yes ("GGT increased")Yes ("Hypermagnesemia" or "Hypomagnesemia" )NoYes ("Hyperkalemia" or "Hypokalemia")
Lipase Glucose (fasting) GGT Magnesium Phosphorus Potassium Sodium	Not applicable, because CTCAE grading includes the information about "asymptomatic"Yes ("Hypoglycemia")Yes ("GGT increased")Yes ("Hypermagnesemia" or "Hypomagnesemia" )NoYes ("Hyperkalemia" or "Hypokalemia")No
Lipase Glucose (fasting) GGT Magnesium Phosphorus Potassium Sodium Total protein	Not applicable, because CTCAE grading includes the information about "asymptomatic"Yes ("Hypoglycemia")Yes ("GGT increased")Yes ("Hypermagnesemia" or "Hypomagnesemia" )NoYes ("Hyperkalemia" or "Hypokalemia")NoNoNoNoNoNoNoNoNoNoNoNoNo
Lipase Glucose (fasting) GGT Magnesium Phosphorus Potassium Sodium Total protein BUN (blood urea nitrogen)	Not applicable, because CTCAE grading includes the information about "asymptomatic"Yes ("Hypoglycemia")Yes ("GGT increased")Yes ("Hypermagnesemia" or "Hypomagnesemia" )NoYes ("Hyperkalemia" or "Hypokalemia")NoNoNoNoNoNoNoNoNoNoNoNoNoNoNoNoNoNoNo
Lipase Glucose (fasting) GGT Magnesium Phosphorus Potassium Sodium Total protein BUN (blood urea nitrogen) Urea	Not applicable, because CTCAE grading includes the information about "asymptomatic"Yes ("Hypoglycemia")Yes ("GGT increased")Yes ("Hypermagnesemia" or "Hypomagnesemia" )NoYes ("Hyperkalemia" or "Hypokalemia")No

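### Fasting glucose and calcium are graded only when low, so high values count as Grade 0 in the CTCAE tables, and SAP 2.8.3 plans no low/normal/high shift table for them

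*SAP*

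**What the plan says.** SAP 5.4 introduces its laboratory tables as an "overview for which lab parameters a CTCAE v5 grade is defined and used in this study". In the Chemistry table the entry for fasting glucose is "Yes ('Hypoglycemia" and the entry for calcium is "Yes ('Hypocalcemia"; neither row has a term for high values. Other rows cover both directions. Magnesium has "Yes ('Hypermagnesemia' or 'Hypomagnesemia", potassium has the corresponding pair, and absolute lymphocytes in the Hematology table take the higher of the decreased and increased grades.

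SAP 2.8.3 sets the grading rules. "The calculation of CTCAE grades will be based on the observed laboratory values only", and "CTCAE Grade 0 will be assigned for all non-missing values not graded as 1 or higher". Tests with CTCAE grades get a worst post-baseline grade table and a shift table in CTCAE grades. The other tests are handled separately: "For laboratory tests where grades are not defined by CTCAE v5.0, results will be categorized as low/normal/high", and the low/normal/high shift table is listed under that group only.

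Protocol 12.5.2 makes the same split. Before the split, however, it has a general sentence on laboratory data that plans low/normal/high shift tables from baseline to the worst value on treatment. SAP 2.8.3 does not carry that sentence over. SAP 2.8 refers to protocol 12.5.2 for the safety analysis, and SAP 4 says the protocol's analyses were not changed.

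**The concern.** A test graded in one direction only is treated as fully graded. It then loses the one table format that would show a shift in the other direction. For glucose that other direction is the high one. Protocol 1.1.1 lists "Cushingoid features, diabetes, cataracts, potassium loss" among the side effects of long-term corticosteroids, and both arms receive high-dose dexamethasone: one cycle in Arm A, one to three in Arm B. Low potassium, from the same list, can be graded under SAP 5.4; high glucose cannot.

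At stake is a patient count in the safety report. Protocol 12.8.1 expects about 24 patients and purely descriptive analyses, so counts by arm are a main safety output. A table showing Grade 0 for glucose in nearly all patients could be read as showing no glucose abnormality, when under these rules it shows only that no value was low enough to be graded.

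**Working it through.** No sample size, power or event count is involved, and the plan states no figure to reproduce. The check applies the SAP's rules in order.

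1. Is fasting glucose a graded test? Yes, because SAP 5.4 marks it so, with hypoglycemia as its only term.
2. Which grade does a value above the normal range get? It cannot meet a hypoglycemia grade, so the Grade 0 rule in SAP 2.8.3 applies.
3. Which shift table does glucose get? As a graded test, only the one in CTCAE grades.
4. What do the tables then show?

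| Patient's glucose, baseline to worst | CTCAE worst-grade table | CTCAE shift table | Low/normal/high shift table |
|---|---|---|---|
| normal, stays normal | 0 | 0 to 0 | not planned in SAP 2.8.3 (would show normal to normal) |
| normal, becomes high | 0 | 0 to 0 | not planned in SAP 2.8.3 (would show normal to high) |

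The first two rows are identical in both planned tables. The trace for calcium is the same, with hypocalcemia as the only term. No step uses the numerical CTCAE limits. The layout of the Chemistry table is broken in the text version, but the pairings for glucose and calcium can be read without doubt.

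**Is the one-sided entry explained?** No. Where SAP 5.4 declines to grade amylase, lipase and INR, it gives the reason: their grades need clinical information. It gives none for leaving out the high side of glucose and calcium.

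**Do the other displays supply the missing count?** Only in part.
- Listings flag each value outside the center's normal range as low or high, so the information exists per patient.
- By-visit statistics include the maximum (SAP 2.1), and boxplots show the distribution. Neither counts patients whose value became high.
- Changes from baseline in SAP 2.8.3 run to the last value on treatment, so a temporary rise can be missed.
- Significant laboratory findings are reported as adverse events and tabulated by preferred term and maximum severity (SAP 2.8.1). Under protocol 10.1.1 a laboratory abnormality is an adverse event only if it causes signs or symptoms, is judged clinically significant or needs therapy.

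**Do protocol and SAP agree?** Not on their face. The general sentence in protocol 12.5.2 would give glucose and calcium a low/normal/high shift table. SAP 2.8.3 would not.

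**The case against.** The strongest reply is that the table is already planned. Protocol 12.5.2 promises low/normal/high shift tables for laboratory data in general, SAP 2.8 refers to that section, and SAP 4 declares no change. Read together, the documents could be said to cover glucose and calcium. This stands as a reason to call the defect one of implementation. It does not remove it: SAP 2.8.3 is the more detailed text and assigns the table only to ungraded tests, and the later part of protocol 12.5.2 makes the same split. A programmer following the SAP would not produce the table.

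Second, low-only grading may be deliberate. Grades are to be based on laboratory values alone, and the CTCAE limits sit in an external source. The documents therefore do not show whether high glucose or calcium can be graded from numbers alone. This stands. A reader might infer that both should be graded in two directions, as potassium and magnesium are, but the documents do not support that. The low/normal/high table is useful either way.

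Third, a reader might infer that the tables hide a steroid-related difference in glucose between the arms. The documents do not establish that such a difference is expected. The diabetes mention in protocol 1.1.1 concerns long-term corticosteroids, not four-day courses. Table 8-1 schedules chemistry on Day 1 of Weeks 1, 3, 5, 7, 9 and 13. If cycles start exactly 14 or 28 days apart, these visits fall on cycle-start days or days off dexamethasone, so scheduled sampling may itself miss short rises. The window for the worst value also differs: 26 weeks in Arm A and up to 12 weeks in Arm B, each plus 30 days. The new table would be descriptive and would not be an even comparison of arms.

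Finally, the documents give no particular reason to expect high calcium here. Calcium is included because the same rule produces the same gap.

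**Conclusion.** The point holds as a minor reporting defect. Under SAP 5.4 and 2.8.3, every glucose or calcium value that is high but not low is Grade 0, so the CTCAE worst-grade and CTCAE shift tables cannot separate it from a normal value. SAP 2.8.3 also departs, without declaring it, from the general shift-table sentence in protocol 12.5.2.

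The effect is confined to those two table types. A reader might infer that high glucose disappears from the safety report. It does not, given the listings, by-visit statistics, boxplots and adverse event tables. The number of patients affected cannot be derived from the documents. The conclusion rests on reading SAP 5.4 as the full list of grading terms in use, which is how that section introduces itself, and on SAP 2.8.3 governing what is programmed. Efficacy results are not touched.

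**What to change.** Reconcile SAP 2.8.3 with protocol 12.5.2. Produce the low/normal/high (low and high) shift table, from baseline to worst value on treatment, for fasting glucose and calcium in addition to the CTCAE tables. Preferably do so for every test graded in one direction only; hemoglobin, white blood cells and fibrinogen are further examples in SAP 5.4. State in SAP 5.4, and in a footnote to the worst-grade and CTCAE shift tables, which direction each grade covers, so that Grade 0 is not read as normal. If the narrower SAP version is intended instead, record it in SAP 4 as a change from the protocol, with the reason.

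The cost is a few extra rows in an existing table format. Fasting glucose and calcium are in the chemistry panel (protocol Table 8-3), and the normal-range flags are already derived for the listings. If the analysis has already been run, one supplementary table is enough.
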